For the purposes of the analysis on dental-related service use and costs among Medicaid beneficiaries, all children participating in Medicaid of elementary school age will be included in the analysis, except for children in participating schools that do not provide informed consent to provide oral health and Medicaid dental service use data.

The Primary Specific Aims are to:

- 1. Determine the non-inferiority of simple vs complex caries prevention for preventing new caries (primary prevention).
- 2. Determine the non-inferiority of simple vs complex caries prevention for arresting current caries (secondary prevention).
- 3. Determine the impact of simple vs complex prevention on child oral healthrelated quality of life
- 4. Determine the impact of once per year vs twice per year care on the arrest and prevention of caries

Notably, toothaches or office based dental care reduces in-class learning time. If the caries prevention programs are as effective as predicted, knowing the time/trade-off will be important. Thus a secondary outcome of the study will be school performance (school absence and student achievement). To insure accurate assessments, program participants will be compared to children in their own schools and to children in NYC "peer schools" not participating in the study. No additional data is collected for educational outcomes from participants.

The Secondary Specific Aims are to:

- 1. Determine the impact of prevention vs no prevention on school absence
- 2. Determine the impact of prevention vs no prevention on standardized test performance
- 3. Determine the impact of simple vs complex prevention on school absence and test performance

The exclusion criteria will be those: (1) not attending participating schools, (2) those attending participating schools without informed consent, or (3) those attending participating schools with informed consent, but without assent and (4) those allergic to silver.

For the purposes of the analysis on dental-related service use and costs among Medicaid beneficiaries, the only excluded groups are (1) children not participating in Medicaid will be excluded and (2) children participating in Medicaid in Caried*Away* schools, but without informed consent to provide oral health and Medicaid dental service use data.

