6.6 Compliance Assessment

This intervention trial depends on protocol compliance by clinicians, not students. We will train and calibrate clinicians during the summer before beginning each school year. To assess compliance, we will use qualitative and quantitative methods together with audit and feedback. Qualitatively, to ensure that the electronic records reflect actual implementation, we will visit each team in the fall and spring of each year for a one-day site visit. During the day, we will monitor adherence to protocol, particularly: student flow, caries diagnosis, and procedures delivered.

Quantitatively, we will use the elementary methods of statistical process control^{27,28}. We will examine four domains: 1) informed consent rates; 2) caries prevalence (e.g.: diagnosis); 3) care provision; and 4) outcomes. We will monitor these domains using electronic records and then verify with in-person site visits. We will start with national averages and standard deviations for school-based informed consent rate (35%), untreated caries prevalence of (21.5%). All children (100%) with permanent bicuspids and molars should receive either silver diamine fluoride (simple prevention) or traditional sealants (complex prevention) and fluoride varnish. All children (100%) with caries on their posterior teeth should receive either silver diamine fluoride (simple prevention).

We will create histograms, Pareto charts, and control charts, at the school, grade, and clinician level to identify common cause and special cause variation. Control limits will be adjusted yearly based on prior year data. If a clinician, school or grade exhibits variation that is out of the control range we will use this audit to work with the clinical team and school to provide feedback. We will continue this process during the school year.

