Longitudinal effects of simple and complex prevention on dental-related service use and costs among Medicaid participants, compared to children in non-participating schools, will be analyzed using difference-in-differences analysis and propensity score matching. The propensity score weighting will be used to match children in participating schools to children in non-participating schools to account for any selection impacting whether a child is at a school participating in the Caried*Away* programs. The propensity score weighting will be used to account for student-level and school-level characteristics impacting whether the student is at a school participating in the Caried*Away* programs.

We will then adapt a published Markov model in combination with threshold analysis to compare the simple and complex prevention programs relative to non-participating schools in net costs and quality-adjusted life-years to determine the cost-effectiveness and budget impact of all three options (simple prevention, complex prevention, no prevention).

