7.3 Subject Population for Analysis

For study outcomes, participants will be analyzed using intent to treat. All participants will be analyzed as randomized in the original randomization, regardless of whether or not they received an intervention.

For dental-related service use and costs, all New York City elementary school-age children enrolled in Medicaid will be analyzed using intent-to-treat.

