8.4 Confidentiality

8.4.1 Protection of Subject Privacy

Subject Confidentiality is strictly held in trust by the investigators, study staff, and the sponsor(s) and their agents.

The study protocol, documentation, data, and all other information generated will be held in strict confidence. No information concerning the study or the data will be released to any unauthorized third party without prior written approval of the sponsor.

All patient information will be stored on password protected tablet (Apple iPad) computers. The iPads are transported by our clinical staff in a locked backpack to and from treatment locations. The iPads are locked each night in a closet on the 8th floor at NYUCD. Participant data is uploaded at the end of each day through a secure transmitting server at NESS. NESS verifies validity of data and erases data from the tablet (Apple iPad). The BEDAC and NESS have additional data security protocols in place for data fidelity and security. Finally, NESS provides de-identified data to the BEDAC and the BEDAC provides de-identified data to the analytic team. Data monitoring, quality assurance, and quality control will be performed by the study Principal Investigators, NESS, the BEDAC, and the NYU Institutional Review Board.

The study monitor or other authorized representatives of the sponsor may inspect all study documents and records required to be maintained by the investigator, including but not limited to clinical data for the study subjects. The PI site will permit access to such records.

The Health Evaluation and Analytics Lab at New York University's Wagner School of Public Service and New York University's School of Medicine will act as a third-party to carry out the the linkage between the oral health outcomes data collected through Caried*Away* and New York Medicaid claims, encounter, and eligibility data. The linkage will be carried out using the Medicaid billing IDs collected through the implementation of the Caried*Away* program and/or first name, last name, date of birth, gender and residential zip code of the student. The Health Evaluation and Analytics Lab (HEAL) will then remove all "facial" identifiers (IDs, addresses, etc.) from the data provided for analysis to construct a HIPAA-defined "limited data set". We will exclude children from the analysis who did not consent to providing their oral health outcomes data and Medicaid claims data.

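### The Medicaid service-use and cost analysis is labelled intent-to-treat on all children, but non-consenters are dropped in participating schools only, so it estimates an effect among enrolled children

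*Combined protocol and SAP*

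**What the plan says.** Section 7.3 gives the analysis population for dental service use and costs: "all New York City elementary school-age children enrolled in Medicaid will be analyzed using intent-to-treat".

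Section 1.2 defines the same population differently. It takes in all Medicaid children of elementary school age, "except for children in participating schools that do not provide informed consent to provide oral health and Medicaid dental service use data", and its exclusion list repeats the rule. Section 8.4.1, on data linkage, adds: "We will exclude children from the analysis who did not consent to providing their oral health outcomes data and Medicaid claims data".

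Section 7.2 says that these outcomes "will be analyzed using difference-in-differences analysis and propensity score matching". It describes the purpose of the propensity score twice. The first time it is "to account for any selection impacting whether a child is at a school participating in the" programme; the second time it is to "account for student-level and school-level characteristics impacting whether the student is at a school participating". Consent is not mentioned in either place. Section 2.2 names matched students in non-participating schools as the comparator.

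**The concern.** An intent-to-treat analysis at school level keeps every eligible child in a participating school, whether or not the family took up the programme. This plan keeps only those whose parents consented. The comparison schools have no such filter, because the consent process runs only in participating schools (Sections 4.2.4 and 6.1.1).

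Parental consent is active, and newly enrolled students may join each year (Section 6.1.1). It may therefore be related to current dental need or care-seeking, which are plausible drivers of Medicaid dental use and cost. A covariate rule aimed at school attendance does not require the analyst to include predictors of consent.

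The secondary objective in Section 2.2, reduced dental service use and costs, depends on this analysis. Section 7.2 goes on to compare simple, complex and no prevention in a Markov model for cost-effectiveness and budget impact. If these estimates are used there, an effect among consenting families could be read as the effect of offering the programme to whole schools.

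**Working it through.** The plan gives no sample size, power or effect size for this analysis, so there is no figure to reproduce. The check is a comparison of the sections, followed by a formula for what difference-in-differences leaves behind.

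**1. Who is analysed**

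| Group | Section 7.3 | Sections 1.2 and 8.4.1 |
|---|---|---|
| Participating schools, consented | included | included |
| Participating schools, not consented | included | excluded |
| Non-participating schools | included | included, no consent condition |

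Section 8.4.1 read alone could seem to require consent from every child. Section 1.2 limits the exclusion to participating schools, and children elsewhere are not asked. The middle row is the conflict: the population in 7.3 cannot stand beside the other two sections.

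**2. What the adjustment is required to cover**

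Membership of the treated group takes two steps: attending a participating school, and having a parent who consents. Section 7.2 ties the covariates to the first step only. Its propensity score for academic outcomes, by contrast, is framed around treatment and gives prior academic performance as an example covariate. The Medicaid paragraph names no covariate and states no check of pre-period trends.

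**3. What difference-in-differences leaves**

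Let c be the share of Medicaid children in participating schools whose parents consent. Let D be the mean outcome of consenters minus that of non-consenters, in the absence of any programme effect.

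- Consenters minus their whole school = m1 - [c × m1 + (1 - c) × m0] = (1 - c) × (m1 - m0) = (1 - c) × D.
- Suppose the comparison pool follows the trend that the whole participating school would have followed without the programme. The residual before matching is then (1 - c) × (D after - D before).

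If D does not change, the residual is zero however large D is. The documents give neither c for this population nor D. The only consent figure is 35% in Section 6.6, a national starting value for process-control charts, so c is varied. Assumed changes in D, in percentage points of yearly dental use, give these residuals:

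| c | D changes by 0 | by 2 | by 5 | by 10 |
|---|---|---|---|---|
| 25% | 0 | 1.5 | 3.75 | 7.5 |
| 35% | 0 | 1.3 | 3.25 | 6.5 |
| 50% | 0 | 1.0 | 2.5 | 5.0 |
| 70% | 0 | 0.6 | 1.5 | 3.0 |

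For example, 0.65 × 5 = 3.25. The sign follows the sign of the change in D, which is unknown. Matching or weighting on covariates that also predict consent would reduce these values. They illustrate the mechanism and do not estimate the bias in this trial.

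**The case against.** The strongest reply is that the propensity score is not fitted to the wrong exposure. Once non-consenters are removed, being at a participating school and being a consented child at one are the same 0/1 indicator in the analysis file. A reader might infer that the score models the wrong selection step and that redefining the exposure as enrolment would repair it. The documents do not support that: the redefinition would give the same variable, and no section says that the score is fitted to a sample that includes the excluded children. What stands is narrower and concerns the choice of covariates.

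A reader might also infer that consenters are simply compared with every child elsewhere. That overstates the plan. Non-participating schools supply the pool, and Sections 2.2 and 7.2 then match or weight on student-level and school-level characteristics within difference-in-differences. Some of those characteristics may predict consent as well.

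A third tempting step is to put 35% consent and an assumed D into (1 - c) × D and report the answer as the bias; D = 10 points would give 6.5 points. That is a raw difference in level between consenters and their own school, before matching and before differencing. Neither input is a value for this trial's Medicaid children, and nothing in the documents shows that D changes over time.

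Finally, Section 7.2 does not rule out prior claims as covariates, and difference-in-differences already uses pre-period outcomes. Both points are fair. They reduce the concern about bias but do not touch the conflict over population and label.

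**Conclusion.** The intent-to-treat label in Section 7.3 does not describe the analysis that Sections 1.2 and 8.4.1 prescribe. This holds at any consent rate below 100% and needs no assumption about bias. The planned contrast is between consenting Medicaid children in participating schools and matched or weighted Medicaid children elsewhere, and it supports a statement about enrolled children only.

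Whether that contrast is also biased cannot be settled from the documents. Stable differences between consenters and non-consenters cancel. Differing trends do not, and the plan neither requires covariates that predict consent nor shows pre-period trends. The size and direction of any remaining bias are unknown, and it may be zero.

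The consequence is limited to a non-randomised secondary objective. It extends to the Markov model only if these estimates are used there, which Section 7.2 does not say. The correction should be made because it is nearly free and changes what the objective can conclude.

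**What to change.** In Section 7.3, replace the statement for dental service use and costs with wording such as: *consenting Medicaid children in participating schools are compared with matched or weighted Medicaid children in non-participating schools; the estimate is an effect among enrolled children*. Limit the service-use and cost conclusion to that population, and do the same for any use of the estimate in the Markov model.

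In Section 7.2, say that the propensity covariates also address selection by consent, and draw them from the claims, encounter and eligibility data that the study already receives (Section 3.3). Show pre-period trends in dental use and cost for both groups. Matching directly on pre-period outcomes within difference-in-differences need not be required: it is debatable, because it can bring in regression to the mean when the groups differ at baseline.

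The cost is protocol wording, a named covariate list and one added display. The youngest children may have short claims histories, which should be reported. The main downside is that the conclusion narrows from all Medicaid children in participating schools to those enrolled.

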7.4 Interim Analysis

There are no interim analyses in this study.

8 DATA AND SAFETY MONITORING PLAN (DSMP)

All protocol amendments, other than minor administrative changes will be submitted in a prospective manner to the NYU School of Medicine IRB for approval and PCORI for notification.

8.1 Informed Consent

Each participating school will obtain consent in accordance with their local circumstances.

The eICF forms were created and are stored using the secure REDCap data management system provided by the NYU Clinical and Translational Science Institute. The REDCap system is HIPAA compliant.

The study administrator uploads all of the informed consent PDF's to NESS via the secure and password protected ShareFile link listed below:

• https://nedental.sharefile.com

NESS then uploads each student's eICF to their electronic dental record in the iPad.

Only select study investigators will have access to the eICF data, which will be stored on REDCap. This includes the principal investigators, the clinical research coordinator, the study administrator, the clinical director, the IRB coordinator and NESS.

8.2 Risk

Risks associated with program participation include potential loss of privacy of the data. The strict security and Data Monitoring plan outlined in this proposal will help reduce this potential risk. Monitoring will be carried out by the PIs and Program Director.

8.3 Implementation

On a daily basis, performance sites will upload data to New England Survey Systems (NESS). On a weekly basis, NESS will upload data to the Biostatistics and Epidemiology Data Analytics Center (BEDAC) formerly the Boston University Data Coordinating Center (DCC). The BEDAC will maintain records for each performance site that includes patients seen and data. The BEDAC will provide weekly reports to the PIs, Program Director, and clinical research associate (CRA) for each performance site that includes the daily reports. These reports will be matched with the MOPs to ensure timely recruitment and data reporting. If results are out of expected range, the CRA will contact the clinical team to determine the cause and develop a plan to resolve the problem. Monthly, quarterly, and yearly reports will be generated by the BEDAC and provided to the PIs and Program Director. The initial reports will include recruitment data, while subsequent reports will include recruitment, retention, and databases for analysis.

8.4 Confidentiality

8.4.1 Protection of Subject Privacy

Subject Confidentiality is strictly held in trust by the investigators, study staff, and the sponsor(s) and their agents.

The study protocol, documentation, data, and all other information generated will be held in strict confidence. No information concerning the study or the data will be released to any unauthorized third party without prior written approval of the sponsor.

All patient information will be stored on password protected tablet (Apple iPad) computers. The iPads are transported by our clinical staff in a locked backpack to and from treatment locations. The iPads are locked each night in a closet on the 8th floor at NYUCD. Participant data is uploaded at the end of each day through a secure transmitting server at NESS. NESS verifies validity of data and erases data from the tablet (Apple iPad). The BEDAC and NESS have additional data security protocols in place for data fidelity and security. Finally, NESS provides de-identified data to the BEDAC and the BEDAC provides de-identified data to the analytic team. Data monitoring, quality assurance, and quality control will be performed by the study Principal Investigators, NESS, the BEDAC, and the NYU Institutional Review Board.

The study monitor or other authorized representatives of the sponsor may inspect all study documents and records required to be maintained by the investigator, including but not limited to clinical data for the study subjects. The PI site will permit access to such records.

The Health Evaluation and Analytics Lab at New York University's Wagner School of Public Service and New York University's School of Medicine will act as a third-party to carry out the the linkage between the oral health outcomes data collected through Caried*Away* and New York Medicaid claims, encounter, and eligibility data. The linkage will be carried out using the Medicaid billing IDs collected through the implementation of the Caried*Away* program and/or first name, last name, date of birth, gender and residential zip code of the student. The Health Evaluation and Analytics Lab (HEAL) will then remove all "facial" identifiers (IDs, addresses, etc.) from the data provided for analysis to construct a HIPAA-defined "limited data set". We will exclude children from the analysis who did not consent to providing their oral health outcomes data and Medicaid claims data.

The Medicaid claims, encounter, and eligibility data (and any other data with personal identifiers) will be maintained on password-protected computers locked inside metal cabinets that would in turn be fastened to office infrastructure, inside locked offices in limited-access buildings. Additionally, the cage will be bolted down to the floor to prevent the physical removal of the hard drive and the data from the cage and from the office. These computers would not have any connection to the internet except briefly periodically to upgrade software. All data backups would be maintained on password protected encrypted external hard drives stored in locked cabinets in locked offices. These specifications are in accordance with the agreement between the Centers of Medicare and Medicaid Services, the NYU School of Medicine, and NYU Wagner for the release and analysis of the New York Medicaid claims data. The PD/PI will use only indirect patient identifiers to minimize the likelihood of identification. No attempts will be made to identify patients in the data, and in the case where subgroup analysis leads to small sample sizes at risk of identification, data will be aggregated or the subgroup enlarged to prevent identification from occurring.

8.4.2 Confidentiality During Adverse Event (AE) Reporting

AE reports and annual summaries will not include subject or group-identifiable material. Each report will only include the identification code.

8.5 Expected Risks

There are no expected risks associated with the clinical interventions proposed in this study. The only risk would be a data breach. The only possibility for a data breach would be the loss or theft of the tablet computers (Apple iPads) used for data collection. However, data is typically synced with NESS before the data collector leaves the school.

The iPads are transported by our clinical staff in a locked backpack to and from treatment locations. The iPads are locked each night in a closet on the 8th floor at NYUCD.

